As the data are collected from databases or registers, outcome or exposure misclassification (information bias) might occur. It is common among such data sources that only the presence of a disease (positive laboratory test result) or an administered vaccination is recorded but not its absence. Consequently, all study subjects without a respective record are considered healthy or unvaccinated. If the chance of being identified and recorded during a healthcare visit as an influenza case depends on the study subject’s vaccination status, this leads to differential misclassification of the outcome. In some small and administratively uniform cohorts, it may be possible to be reduced by implementing strict criteria for taking respiratory samples and other diagnostic procedures in the population. However, if databases are based on established routine health care practises and if the population is very large, it is more difficult to control this bias. Additionally, if vaccinations are given by various providers, they all should be covered by the available data sources to avoid an underestimation of the vaccination coverage.

Due to the population based cohort design, the risk of upfront selection bias at recruitment is minimised, although not removed. However, the data source defining the study cohort must not depend on the influenza vaccination data source, and ideally a cohort should be defined, where all individuals have equal chance to be detected with the exposure and outcome events. Restricting the study cohort to a specific subpopulation does not add selection bias but reduces the generalisability of the findings.

The available databases may compromise these ideal requirements. During the DRIVE collaboration process, the potential confounders and biases as well as strategies to reduce their impact in VE studies will be identified by a systematic literature review (DRIVE D2.2), and the protocol may be updated accordingly.

Sensitivity analyses

When appropriate, sensitivity analyses may be conducted to test different outcome definitions, different exposure definitions or exclude a subset of the data (e.g. different outcome onset and disease episode definitions, different definitions for non-specific outcomes defined in the study site level SAP, different influenza testing methods, VE against matched and non-matched vaccine strains, VE for one and two doses of injectable vaccines and for 0.25 ml or 0.5 ml doses in children, ‘potential vaccination’ status)

The most important sensitivity analyses to be used in pooled analysis will be described in the study site level SAP (Annex 2), but sensitivity analyses may also be planned after the data has raised additional questions.

Adverse events reporting

This is a non-interventional epidemiological study for assessing the effectiveness of routine influenza vaccination, using secondary data from existing databases. No data of adverse events will be collected or reported. Ethical evaluation and other relevant approvals

Each study site will comply with the relevant international, national and regional regulations and ethics requirements. Special attention will be paid to data protection. Where applicable, the local processes of ethical evaluation and relevant approvals to use the databases and obtaining informed consent, if applicable, will be adhered to.

- *If an informed consent is needed, the following information should be specified: Who is responsible for the study, aim of the study, nature of processed data, purposes of processing, purpose of the use of the data, recipients of possible data transfers, rights of data subject & consequences of not accepting the informed consent.*

DRIVE will collect copies of the appropriate approvals from each site and submit them to IMI. If no formal approvals or ethical review is required and not available, a statement signed by the responsible investigator of the study site with rationale of this must be provided..

- *Each study site to describe the processes of ethical evaluation and approvals needed, compliance with the relevant legislation and guidelines and principles of data protection.*
- *Each study site to provide a copy of the ethical approval, or a statement on why this is not needed.*

Dissemination of results

The study site will remain the owner of the data and may disseminate the study results according to their local practices. The data will also be submitted to DRIVE WP7 for common European pooled and/or meta-analyses. EFPIA members do not have access to this data. DRIVE will disseminate the results of its analyses according to its Communications plan (DRIVE D5.4).

Study reports

Each study site will write a report at the end of the season and submit it to DRIVE WP7. DRIVE WP7 will write a final report presenting the results of the pooled analysis.

Both study site- and consortium level reports are to follow the template provided by DRIVE D4.3: Report templates.

Publications

Study sites may publish their own data independently from DRIVE. If DRIVE funds were used to collect the data, this should be acknowledged in the publications.

Authorship of joint DRIVE publications follows the rules of International Committee of Medical Journal Editors (ICMJE).

Logistical aspects

Study sites

A study site is any entity that administers and conducts the individual studies according to the regulations and ethical codes of EU and the country and institutions involved. The study site collects the data and provides it to DRIVE as a whole. EFPIA members do not have access to this data. Study sites may be local, regional or national; examples include GP and hospital networks having access to databases from established population based cohorts, influenza surveillance schemes and public health institutes utilizing routine health care, social service and demographic databases.

Study leader

In each study site, a study leader (principal investigator) will coordinate and be responsible for the study at the study site level and act as focal point towards DRIVE. The WP7 of DRIVE is in charge of the pooled and/or meta-analysis across several study sites.

- *Each study site to introduce the study leader and the study team with brief CVs and Declarations of Interest.*

Standard operating procedures and quality issues

Standard operating procedures (SOPs) developed and harmonised in DRIVE should be adapted to the individual studies and used by investigators during all the steps of the study for identification of study subjects, data collection, laboratory methods, data entry, monitoring, etc. as provided in DRIVE. Guidelines of definitions for the study variables will be included in the generic study site level analysis plan (SAP), for harmonisation of the methods between the study sites (Annex 2).

Potential systematic or major deviations from the SOP and generic study site level SAP should be described for further development of the methodology and for interpretation of the results. DRIVE WP 2 and WP 3 will further evaluate the quality of the studies and develop guidelines and methods for improving the quality.

- *Each study site to adapt DRIVE study SOPs and guidelines to be used by the study team and provide a summary of systematic or other major deviations from them to WP7, to be stored*

Training

- *Each study site to describe the trainings to be organised*

Changes to the protocol

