To measure seasonal IVE against medically attended laboratory-confirmed influenza, by vaccine brand, then by vaccine type (e.g. by antigen preparation strategy, number of virus strains, adjuvant; see section *Exposure*), then by overall influenza vaccination.

Secondary objectives

To estimate IVE (brand-specific, type specific and total, if possible) against laboratory-confirmed influenza by:

- age group (children, young adults and elderly; the age groups will be further defined in the generic study site level SAP)
- influenza virus type (A, B) and/or subtype (A/H1N1, A/H3N2) and lineage (B/Victoria, B/Yamagata)
- severity/level of health care required (primary health care, hospitalisation)
- risk groups / target groups for vaccination, e.g
 - pregnant women
 - healthcare workers
 - any chronic condition (see Annex 1 and Annex 2)
 - specific chronic conditions (see Annex 1 and Annex 2)
- time since vaccination
- time window in the epidemic season (early, middle, end)(see section Study period)
- previous influenza vaccinations (one or preferably more previous seasons)

To estimate IVE (brand-specific, type specific and total, if possible) against non-specific outcomes with public health relevance, e.g.

- suspected or diagnosed influenza requiring medical attention (primary care and/or hospitalisation)

- respiratory infection, pneumonia or other respiratory conditions requiring hospitalisation, intensive unit care, or leading to death other non-specific outcomes such as cardiovascular events or deterioration of chronic conditions

To estimate brand-specific, type specific or total IVE against laboratory confirmed influenza and/or unspecific outcomes across several seasons, considering the local circulation of the strains and clades detected by the virus surveillance systems, if possible

The details of the analyses will be prescribed in the generic study site level SAP, updated annually according to the characteristics and structure of data available at the participating study sites

Methods

Study design

In each participating study site, a cohort study using secondary data from existing databases or health care registers (see section *Cohort of interest*). To reach appropriate sample size for assessing brand-specific VE, the data from individual studies will be pooled.

Study setting

The population-based study setting is defined by each study site, based on the available data.

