- *Each study site to describe the source population and definition of the study cohort Each study site to specify the target groups for which influenza vaccination is recommended, which vaccines are used in the database catchment area, and how the choice of vaccine brand happens*

Study period

The study follow-up will start before the seasonal influenza vaccine is available and before the influenza virus circulation begins in the country/region, to ensure that all vaccinations and all outcomes in the defined cohort are captured. If only aggregated data will be collected that does not allow the shortening of the study subjects' follow-up as part of the statistical analysis, the follow-up may be restricted to the time the vaccine first becomes available or the virus circulation starts, whichever occurs first. The study period will finish at the end of the influenza season.

- *Each study site to specify the study period: the definition of the beginning and end of the study period*
- *Each study site to specify the early, middle and end of the influenza epidemic at the study site according to the information provided by the local influenza surveillance system.*

For the pooled analysis, a harmonised minimum period will be defined (e.g. from week 40 till week 20), but if needed, it will be extended to fully cover the vaccination campaign and the epidemic in each study site. Definition of shorter time periods (e.g. early, middle and end season) will be developed to take into account differences in influenza activity over time and probable development of immunity in unvaccinated population through encounters with the circulating viruses

For addressing the secondary objective of estimating influenza vaccine effectiveness over several seasons, multiple study periods will be combined. If possible, the information from the local surveillance systems of major circulating strains in the study regions will be considered in the analysis. The details of the analysis will be described in the generic study site level SAP.

Study population and follow-up

Cohort of interest

The study cohort comprises the characterised by place of residence, or catchment population of a health care service providing the relevant information for the analyses. The databases may also be characterised by or restricted to e.g. age, or medical, physiological or occupational conditions (e.g. pregnancy, health care workers, other risk/target groups).

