Multiple imputation methods are rarely used to correct for missing data in cohort studies, but it may be applied for categorical background factors at start of the follow-up, assuming that the missingness does not depend on unobserved variables. A sensitivity analysis may be carried out comparing the IVE estimates based on the multiple imputation approach with the IVE estimates based on a restricted subpopulation with full background data available.

Addressing confounding & bias

Observational influenza vaccine effectiveness studies are prone to several sources of confounding and other types of bias. Please also refer to section *Potential confounders and effect modifiers* and DRIVE D2.2: Systematic review of the sources of confounding, bias and strategies to manage their impact in influenza vaccine effectiveness studies.

- *Negative confounding* refers to biases that reflect the fact that high risk groups (people more likely to develop severe complications) will be more likely to be vaccinated and therefore reduce VE. If negative confounding is present, the VE will be underestimated. Adjustment for potential negative confounding factors documented in the study (e.g. presence of chronic diseases) will minimise negative confounding.
- *Positive confounding* refers to biases that reflect a ‘healthy vaccine effect’. People with a healthy lifestyle will be more likely to accept vaccination, thus leading to an increase of measured VE. Or, similarly, people being in a state of “extreme frailty” will not be offered vaccination. If positive confounding is present, VE will be overestimated.

Thus, methods should be developed to recognise, and if possible, to model both the frailty (e.g. number and severity of underlying conditions) and the healthcare seeking behaviour adequately and to balance possible differences between the vaccinated and the unvaccinated in the study cohort e.g. by applying the propensity score methodology. Propensity score is the probability of being vaccinated given the baseline information. It is estimated as a unique value for each study subject and used in the VE model to adjust for baseline differences between the non-vaccinated and vaccinated, e.g. in quintiles (please, refer also to Annex 2 and DRIVE D7.3).

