Annex 1: The dataset

Annex 1 defines the data elements to be used for estimating brand-specific VE in a population based cohort study using secondary data from pre-existing databases. The minimum dataset is marked with an asterisk(*), but preferably the most important covariates to adjust for will be included. According to these data elements, the analysis database will be developed to include the defined outcome events by person months vaccinated, (partially vaccinated) and unvaccinated, considering the events leading to right-censoring, and the covariates needed for adjustment or stratification.

The database may alternatively be structured for aggregated data, initially based on these data elements.

Instructions for harmonisation of the variables and the structure of analysis database will be provided in the generic study site level Statistical Analysis Plan (SAP), Annex 2. Season-specific updates in Annex 2 will be implemented to Annex 1, if needed.

DRIVE – The dataset for estimating VE in a population based cohort study using secondary data from pre-existing databases. The minimum data set is marked with an asterisk(*)�.

	Variable	Description	Format	Values and coding	Example
General	idcountry*	Country code defined in ISO 3166-1 alpha-2	2 letters text		Finland
	id*	Patient or aggregate identification number	Unique integer		12345678
	cohort*	Cohort name	Text		THL
	region*	Region name	Text		Pirkanmaa
	dataset*	Data set name	text		Elderly
	sex*	Sex	Numeric (Binary)	0=Female 1=Male	0
	dob* (alternatively age)	Date of birth or age at the start of the follow-up (children: months; adults:years)	dd/mm/yyyy	Date between the date of birth of the oldest and youngest study subject	01/01/1960

The follow-up	startdate*	Date of the start of the study period	dd/mm/yyyy	Date within the study period	30/12/2017
	enddate*	Date of the end of the study period ^a	dd/mm/yyyy	Date within the study period	30/12/2017
	middledate	Date separating the early and the middle epidemic season	dd/mm/yyyy	Date within the study period	30/12/2017
	latedate	Date separating the middle and the end epidemic season	dd/mm/yyyy	Date within the study period	30/12/2017
	death*	Died during the follow-up	Numeric (Binary)	0=No 1=Yes	1
	deathdate*	Date of death ^a	dd/mm/yyyy	Date within the study period	30/12/2017
	moved(*)	Moved out of the cohort catchment area during the follow-up	Numeric (Binary)	0=No 1=Yes	1

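### Non-specific outcomes are by default counted over the whole study period, and the dataset lacks the epidemic-start date needed to limit them to circulation weeks or to use the weeks before as a bias check

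*Combined protocol and SAP*

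**What the plan says.** **Period.** Under Study period, "The study follow-up will start before the seasonal influenza vaccine is available and before the influenza virus circulation begins in the country/region", and "The study period will finish at the end of the influenza season". For pooling, a harmonised minimum period is to be set ("e.g. from week 40 till week 20"), which may be lengthened at a site but is not described as being shortened. Individual follow-up, under Statistical analysis, runs from the start of that period to the first outcome, censoring or the end of the period, with no distinction between outcomes.

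**Restrictions.** The one explicit restriction is optional and concerns aggregated data "that does not allow the shortening of the study subjects' follow-up as part of the statistical analysis". For such data, "the follow-up may be restricted to the time the vaccine first becomes available or the virus circulation starts, whichever occurs first". Study period also promises shorter periods reflecting influenza activity and asks each site to specify the epidemic phases from local surveillance. Under Secondary objectives, the early/middle/end analysis is listed only for laboratory-confirmed influenza.

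**Outcomes.** The non-specific outcomes range from suspected or diagnosed influenza to "respiratory infection, pneumonia or other respiratory conditions requiring hospitalisation", death and cardiovascular events.

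**Dataset.** Annex 1 holds the start and end of the study period as minimum fields, plus two optional cut dates. One is the "Date separating the early and the middle epidemic season"; the other separates middle from end. There is no date for the start of the epidemic.

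**Bias.** Addressing confounding & bias describes the healthy-vaccinee effect and concludes: "If positive confounding is present, VE will be overestimated". Neither that section nor Sensitivity analyses mentions using the weeks before circulation.

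**The concern.** Laboratory-confirmed influenza largely confines itself to weeks when virus circulates. Pneumonia, respiratory admission, cardiovascular events and death occur all year, and outside circulation influenza vaccination cannot prevent them by preventing influenza. Counting those weeks adds events on which the vaccine has no such effect, so relative VE falls as their share rises. That share differs by site and season, so pooled estimates would mix different dilutions. If a first-event definition is chosen, which the plan leaves open, a person with pneumonia in autumn would also be lost to the epidemic weeks.

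The same weeks have a use that the plan does not take up. Before circulation the expected vaccine effect is zero, so an apparent VE there points to residual differences between vaccinated and unvaccinated people. Because the expected VE against non-specific outcomes is low, a modest residual difference could make up most of the estimate without being noticed.

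**Working it through.** **The plan's own figures.** The sample-size section and Annex 3 cover laboratory-confirmed influenza only, and they are not in dispute here. For example, equation (3) with 5,000 subjects, 50% coverage, 5% attack rate and VE 50% has 62.5 and 125 cases among 2,500 subjects per group. The lower limit is 1 − 0.5 × exp(1.96 × √(1/62.5 − 1/2500 + 1/125 − 1/2500)) = 32.6%, consistent with the stated limit above 25%. No figure is given for non-specific outcomes.

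**Inputs.** From the documents:
- Example pooled period, weeks 40 to 52 plus weeks 1 to 20: 13 + 20 = 33 weeks.
- VE against influenza 50%, the planning value.

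Assumed, because the documents are silent:
- Circulation lasts c = 8 to 16 weeks.
- Influenza causes a fraction f = 10 to 30% of outcome events among the unvaccinated in those weeks.
- The background rate is constant, set to 1 per week.

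**Formulas.** Influenza events over the season are F = c × f/(1 − f).
- VE in circulation weeks = 0.5 × f.
- VE over the whole period = 0.5 × F/(33 + F).
- VE on calendar-matched vaccinated time, assuming no vaccinated person-time in the first six weeks = 0.5 × F/(27 + F).

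| c | f | F | Circulation weeks | Whole period | Calendar-matched |
|---|---|---|---|---|---|
| 8 | 10% | 0.89 | 5% | 1.3% | 1.6% |
| 8 | 20% | 2.00 | 10% | 2.9% | 3.4% |
| 12 | 20% | 3.00 | 10% | 4.2% | 5.0% |
| 16 | 20% | 4.00 | 10% | 5.4% | 6.5% |
| 16 | 30% | 6.86 | 15% | 8.6% | 10.1% |

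At f = 20%, two sites with the same 10% in circulation weeks would report 2.9% and 5.4% over the whole period, purely because circulation lasts 8 weeks at one and 16 at the other.

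**Follow-up ending with the season.** In the central case (c = 12, f = 20%), let 8 vaccinated weeks precede a 12-week epidemic and let follow-up stop when it ends. VE is then 0.5 × 3/(20 + 3) = 6.5%, against 10%.

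**Residual bias.** Suppose vaccinated people have a rate ratio of 0.9 for reasons unrelated to the vaccine (assumed). In the central case:
- Pre-circulation weeks: 1 − 0.9 × 1 = 10%, where 0% is expected.
- Circulation weeks: 1 − 0.9 × 0.90 = 19%, where 10% is true.
- Whole period: 1 − 0.9 × (1 − 0.0417) = 13.75%, where 4.2% is expected. About (13.75 − 4.17)/13.75 = 70% of this estimate is bias.

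With a rate ratio of 0.8 and f = 10%, circulation-week VE reads 1 − 0.8 × 0.95 = 24% for a true 5%, and the pre-circulation weeks read 20%. Restricting the window therefore removes dilution but not bias; the pre-circulation estimate is what reveals the bias.

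**The case against.** The strongest reply is that the quoted period is a window for capturing data, not a settled analysis rule. Study period implies that follow-up can be shortened where individual data exist, and it promises shorter periods reflecting influenza activity. Annex 2 is a declared placeholder, to be written once the sites' databases are understood. This stands: a reader might infer that the plan has fixed whole-period counting, and the documents do not support that. It is the default if nothing further is written. But the promised periods are not linked to non-specific outcomes, and the dataset lacks the date needed to build them.

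A reader might also infer that the epidemic's end is missing. It is not wholly missing, because the study period is to finish with the season and its end date approximates the epidemic's end. The pooled minimum period may still run past it. Only the start is clearly absent, although sites must consult surveillance to define the phases anyway.

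Time-dependent vaccination status and a common start date mean that a Cox model on time since start ignores weeks in which nobody is yet vaccinated. That stands, and it is why the central case is better put at 4.2 to 5.0%, or 6.5% if follow-up ends with the season. Calendar alignment removes the pre-vaccine weeks, but not the vaccinated weeks before or after circulation.

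Finally, the Background section expects low VE against non-specific disease and values total burden, so a whole-season estimate is a legitimate quantity. That supports keeping it as a secondary analysis. The plan's only effect measure is relative VE, which depends on the window.

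**Conclusion.** The point holds as a gap in the default rule and in the dataset, confined to secondary outcomes. Under the assumed inputs, VE of 5 to 15% in circulation weeks becomes 1.3 to 8.6% over 33 weeks, or 1.6 to 10.1% when calendar-matched. These are ranges under assumptions, not estimates for any site. They apply to outcomes with a large non-influenza background and less to suspected or diagnosed influenza, where the influenza share may be higher.

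Two stronger readings should be resisted. One is that reported VE will be too low: healthy-vaccinee bias acts upwards and can exceed the dilution, so the net direction is unknown. The other is that the primary objective is compromised: laboratory-confirmed influenza has no comparable background outside circulation, so this dilution does not reach it.

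**What to change.** 1. Add epidemic start and end dates, per site and season and taken from the local surveillance already used for the phases, to the Annex 1 minimum dataset.
2. In Annex 2, for non-specific outcomes with individual or person-time data, make circulation weeks the main risk window, with vaccinated and unvaccinated time aligned by calendar time. Keep the full period as a secondary burden analysis. Sites supplying aggregates should split the counts at these dates when extracting them, since the split may not be recoverable later.
3. Fit the same adjusted model to the weeks before epidemic start, counting vaccinated time only after the 14-day window. Report that estimate with its 95% CI beside each non-specific VE.
4. State that it is a diagnostic to guide interpretation. It should not be a correction factor, because bias need not be equal before and during circulation. Nor should it be an automatic bar on interpretation, because any departure from zero may be chance.

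The cost is two site-level dates and one extra model run per non-specific outcome on data already collected. The main window will contain fewer events, and the control estimate will be imprecise where circulation starts soon after the campaign.
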